Protocol and Statistical Analysis Plan

Title: Effect of the DentalVibe injections system on pain during local anesthesia injections in children
(0661-17-FB)

PI: [name]
NCT03374982
Approved 01-11-2018

Summary

The purpose of this study is to compare self-reported pain scale measurements using the Wong-Baker FACES pain rating scale from an experimental group (local anesthesia injection with DentalVibe system) and a control group (traditional local anesthesia injection with DentalVibe system turned off) in children. Eligibility: Children age 5-11 years old who require local anesthesia for bilateral dental treatment at UNMC pediatric dental clinic. Children must understand and speak English. Interventions and evaluations: Each patient will have two separate restorative appointments where the DentalVibe will be used during local anesthetic injections. One appointment the DentalVibe will be turned on and one appointment the DentalVibe will be turned off. After each injection the child will be shown the Wong Baker FACES Pain Rating Scale and asked to pick a face associated with their level of hurt during the injection. Follow-up: All children will be followed up with any necessary recommended dental treatment.

Purpose, Background and Rationale

The purpose of this study is to compare self-reported pain scale measurements using the Wong-Baker FACES pain rating scale from an experimental group (local anesthesia injection with DentalVibe system) and a control group (traditional local anesthesia injection with DentalVibe system turned off) in children.

An important aspect of behavior guidance in pediatric dentistry is the control of pain during dental procedures. There can be anxiety and discomfort associated with some dental procedures. Anxious patients feel more pain than less anxious patients.¹ Dental procedures can be carried out more effectively if a child is not in pain. The use of local anesthetic is generally indicated when teeth require restorative treatment or extraction. Dental injection is the dental procedure that produces the greatest negative response in children.² If a child experiences pain during a dental procedure, their future as cooperative dental patients may be damaged.³ Children who have traumatic dental experiences are more likely to avoid the dentist as an adult.^{4,5}

Different techniques have been proposed to decrease pain and anxiety during local anesthetic administration. Distraction by use of audiovisual glasses have been shown to reduce the pain associated with the injection of local anesthesia.⁶ Another study showed cooling the injection site before local anesthetic injections reduced pain perceived by pediatric patients.⁷ The Wand, a computer delivery system that provides precise injection flow rate, can provide less painful injections when compared to the conventional local anesthesia in pediatric patients.⁸

According to the Gate theory, proposed by Wall & Melzack in 1965, pain can be reduced by activation of nerve fibers that conduct non-noxious stimuli.^{9,10} Vibration stimulus can decrease pain during dental local anesthetic administration.^{11,12} Numerous devices have been developed to cause stimulation of the mechanoreceptors during injections to reduce pain.

The Vibraject is a device that attaches to a traditional dental syringe and transfers vibrating stimulus to the needle. In the study by Roeber, the Vibraject did not provide any benefit over a conventional approach to anesthesia injections in children. This may have been due to the vibrations targeting the wrong location.^{13,14} The Gate Theory suggests pain can be blocked by pressure or vibration to the surrounding tissue but not necessarily the exact same tissue where the nociceptive stimulus is directed. In contrast, the DentalVibe targets tissues surrounding the injection site, so it might produce better pain relief.

More recently the DentalVibe has been proposed to reduce pain during local anesthetic administration. The device is handheld and delivers vibration to the tissues around the injection site. This device can replace the dental mirror or operator's finger to acts as a check and/or lip retractor. The DentalVibe allows for no changes in the traditional local anesthetic injection technique, patient position and time involved. In the study by Ching, the use of the DentalVibe injection system significantly reduced pain associated with infiltration injections of local anesthesia in adolescents.¹⁵ Studies of its use in children have had mixed results.¹⁶⁻¹⁷ The study by Raslan & Masri did not show significant reduction in pain with use of the DentalVibe. This study was conducted on subjects in a similar age group but only subjects with positive or absolute positive on the Fankl behavior rating scale were included. This raises the question of the influence of the DentalVibe on subjects with various levels of cooperation.¹⁸

This study will be a systematic replication of the study by Ching. The population will be younger and subjects will not be excluded for poor behavior. The purpose of this study is to compare self-reported pain scale measurements from an experimental group (local anesthesia injection with DentalVibe) and a control group (traditional local anesthesia injection with DentalVibe system turned off) in children ages 5-11.

Subjects

The justification for the inclusion of children in this research is that typically children experience discomfort during local anesthetic administration during dental appointments. 30 subjects between ages 5-11 should be an adequate number of subjects to complete the research. A power analysis will be performed to verify the total number of subjects needed to complete the research in order to achieve the scientific objectives of the study.

Inclusion Criteria

The specific inclusion criteria are children between the ages of 5-11 who require dental treatment that requires bilateral local anesthesia on the maxilla or mandible. Subject must understand and speak English.

Exclusion Criteria

The specific exclusion criteria are that no children with the presence of medically or developmentally compromising conditions (autism, cerebral palsy, moderate/severe asthma); history of chronic disease (seizure disorder, cardiac disorder, hematological disease, endocrine disorder, liver disease, renal disease) and currently taking medication which contraindicated the use of local anesthesia. Non-english speakers will also be excluded. Subjects who require oral sedation or general anesthesia for treatment due to behavior or medical history will be excluded.

Methods

This study will be a systematic replication of the Ching study. The differences will be:

Age range of the subjects

Subjects will not exclude subjects with negative Frankl behavior ratings

All subjects will receive nitrous during both restorative appointment due to the age of the subjects.

Administration of nitrous oxide is commonly practiced in pediatric dentistry with patients of this age group. From McDonald & Avery (2016) eighty-five percent pediatric dentist use inhalation of nitrous

oxide and oxygen. It is used to reduce anxiety, produce analgesia, and enhance effective communication between a patient and health care provider.

Up to 50 children between the ages of 5-11 years will participate in this randomized, controlled, split-mouth study. There will be no gender restrictions used in this study. Participants will be recruited from a continuous sample of patient seen at the UNMC pediatric dental clinic and will be selected based on their need for dental treatment. Each child will have 2 separate dental appointments. Written consent will be obtained from parent or guardian prior to first restorative appointment. Verbal consent will be obtained prior to second restorative appointment. [name] will be the provider for every patient. The same dental assistant will be used for each appointment. All treatment will be completed in the same private quiet room. Both [name] and the dental assistant will wear the same color scrubs and black lab jackets during all appointments. One appointment patient will receive local anesthetic dental injection with the DentalVibe turned on and at one appointment the child will receive local anesthetic dental injection with the DentalVibe off. Used strictly as a check/lip retractor. The child will be randomly assigned via a random number generator to either the DentalVibe on or off during the initial appointment. During the DentalVibe turned on appointment, the DentalVibe will be introduced to each child to make him/her familiar with the vibration sensation. All patients will receive 5 mins of O₂, then N₂O will be titrated up to 50%N₂O/50%O₂.

When appointment is complete the child will receive 5 mins of 100% O₂. At both restorative appointment a cotton tip applicator with 20% Benzocaine topical anesthetic gel (Patterson) will be administered for 1 min. 2% Lidocaine HCl with 1:100,000 epinephrine (Patterson Dental) will then be deposited using a medium-length (0.4mm) with 27-gauge short needles. Local anesthetic injections will be referred to as sleepy juice. Buccal and lingual infiltration will perform on the maxilla. Mandibular blocks will be performed on the mandible. One cartridge of local anesthetic will be used at each appointment. After administration, patient will be shown the Wong Baker FACES pain rating scale and asked to rate the amount of discomfort experienced during the injection by pointing to the face or number.

The following manuscript will be used:

Each face represents a person who has no hurt, or some hurt, or a lot of hurt.

Face 0 doesn't hurt at all.

Face 2 hurts just a little bit.

Face 4 hurts a little bit more.

Face 6 hurts even more.

Face 8 hurts a whole lot.

Face 10 hurts as much as you can imagine, although you don't have to be crying to have this worst pain. Touch the face of the hurt you felt when I gave you the sleepy juice.

After child has rated pain [name] will continue with restorative treatment. The same process will be followed at the second appointment. Appointments will be scheduled 3-4 weeks apart.

The statistical methods to analyze the data will likely be a combination of measures of central tendency, descriptive stats, t-tests and correlations using SPSS version 2.2.

Risk

Potential risks are minimal. There is considered to be no more risk to a child beyond what is normally associated with local anesthetic injections. All potential participants will still require dental treatment requiring bilateral local anesthetic administration in the dental clinic. The only change in procedure for

consenting individuals will use the DentalVibe injections system to aid in local anesthetic administration. The DentalVibe system acts as a cheek and/or lip retractor which is often performed with the dental mirror or operator's fingers. [name] will monitor the subject's behavior by observation. This will help ensure the safety of the subjects.

Monitoring/Auditing/Analysis

[name] will conduct procedural checks in which the dentist (PI) implementing the procedures will be monitored to ensure appropriate consent is obtained and treatment protocol is being followed. The procedural fidelity checks will occur weekly.

[name] will perform ongoing data and safety analysis. She will administer the local anesthetic with the DentalVibe injections system and present the Wong-Baker FACES pain rating scale to the children after local administration.

Data analysis will occur every time a child is administered anesthetic. Data analysis will occur when the child is asked to evaluate his/her own pain rating.

Benefits

The potential benefits to the subject that may reasonably be expected from participation in the research is that less pain may be felt during local anesthesia injection. Potential benefits to society include the possibility of identification of an effective device to reduce pain during local anesthetic injections in children. This could lead to better behavior and more positive experiences in the dental clinic.

Recruitment

All subjects will be new or existing patients of the UNMC pediatric dental clinic. Research staff will have ethical access to potential subjects because [name] has a clinical relationship with the potential subjects. Participants will be recruited from a continuous sample of patients who are scheduled for new patient or recall appointments at the UNMC Pediatric Dental Clinic. The children's parent or guardian will be informed of the research. If parent/guardian chooses to have their child participate, the research will be further explained. A treatment appointment will then be made with [name]. If the parent/guardian chooses not to have their child participate, a treatment appointment will still be scheduled with [name] or one of the other providers.

Informed Consent

The location where informed consent will be obtained in the consultation room located in the UNMC pediatric dental clinic. The environment will be conducive to discussion. The consultation room is a private and quiet room located behind closed doors. [name] will be the only person involved in the process of consenting the parent or guardian about their child's participation in this study. Her responsibility will be to properly inform the parent or guardian about the research. Approximately 10-15 minutes will be allotted to the process of consent. The process of consent for parents or guardians who are likely to be more vulnerable to coercion or undue influence may include but are not limited to appointment of a subject advocate, involvement of the subject's family or friends, counselors or other confidants, reading the consent to the parents or guardians, and use of teaching aids. [name] will question the parents or guardian concerning his/her understanding of all the elements of informed consent. At the second treatment appointment [name] will get verbal consent for the child to continue to participate in the study before starting the appointment. During the appointment when the DentalVibe injection system is turned on, the DentalVibe will be introduced to each child to make

him/her familiar with the vibration sensation prior to use during local anesthetic injections. Tell-show-do will be used as a behavior guidance technique during all dental appointments.

References

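### The draw settles only which visit is ON; the plan does not conceal it or require side, tooth and injection type to be set first, so side could be matched to condition

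*Combined protocol and SAP*

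**What the plan says.** The design is introduced in the Methods section: "Up to 50 children between the ages of 5-11 years will participate in this randomized, controlled, split-mouth study". Each child attends twice, 3 to 4 weeks apart, once with the device on and once with it off. The allocation rule is one sentence: "The child will be randomly assigned via a random number generator to either the DentalVibe on or off during the initial appointment". The second visit takes the other state.

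The plan is silent on these points:
- when the draw is made relative to treatment planning;
- who holds the sequence, and whether it is concealed;
- whether the draw is simple or blocked;
- which side or tooth is treated at which visit, and whether that is written down before the draw.

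Eligibility (Inclusion Criteria) is a need for bilateral anaesthesia in the upper or lower jaw. Matched teeth or lesions are not required. Methods assigns infiltration to the upper jaw and a block to the lower.

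Methods has a single provider for every child. Monitoring/Auditing/Analysis says that the person who injects also presents the pain scale. The same section provides for someone to check the dentist's procedures: "The procedural fidelity checks will occur weekly".

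The analysis is described only as descriptive statistics, t-tests and correlations, with no term for visit, side or jaw. The sample size appears as "30 subjects between ages 5-11 should be an adequate number of subjects to complete the research" under Subjects and "Up to 50 children between the ages of 5-11 years will participate" under Methods.

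**The concern.** Giving each child both conditions removes differences between children. It does not remove differences between the two sides of one child's mouth. In a split-mouth trial, something must make the pairing of side with condition independent of what the operator expects.

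Randomising the order does that only if the side planned for each visit cannot respond to the draw, and nothing in the plan ensures this. The operator uses the device and so knows its state. If she also knows the assignment when choosing the visit-1 side, she could, without intending it, pair the easier side with one condition. That one choice largely settles visit 2 as well, and so fixes the whole contrast for that child.

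The resulting bias would go straight into the mean ON-OFF difference. It does not shrink with more children, and a larger sample makes a false finding more likely. It cannot be repaired after data collection if the planned sides were never recorded.

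**Working it through.** **Plan's own figure.** There is none to reproduce for allocation balance or bias. The sample size cannot be re-derived either, because alpha, power, effect size and SD are absent and the calculation is deferred: "A power analysis will be performed to verify the total number of subjects needed to complete the research". I use n=30 and n=50, the two figures in the documents.

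**Assumptions (none from the documents).**
- s: pain difference between a child's two sides, 1 to 2 points, where one face on the scale is 2 points.
- q: share of children whose easier side gets ON, 0.60 to 0.75, where 0.50 means no steering.
- SD of within-child differences: 3 points in total, varied from 2 to 4.
- Paired t-test, two-sided 5%, no true device effect.

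**Step 1: bias.** Bias in favour of ON = s × (2q − 1).
- Low end: 1 × (2 × 0.60 − 1) = 0.2 points.
- Middle: 2 × (2 × 0.65 − 1) = 0.6 points.
- High end: 2 × (2 × 0.75 − 1) = 1.0 point.

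**Step 2: chance of a false finding that ON is better.** Noncentrality = bias × √n / SD. The probability is the upper tail of the noncentral t with n − 1 degrees of freedom, beyond 2.045 (n=30) or 2.010 (n=50). With no bias it is 2.5%.

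| Bias (SD 3) | Noncentrality, n=30 | Probability, n=30 | Noncentrality, n=50 | Probability, n=50 |
|---|---|---|---|---|
| 0.2 | 0.365 | 5.4% | 0.471 | 6.7% |
| 0.6 | 1.095 | 18.4% | 1.414 | 28.3% |
| 1.0 | 1.826 | 42.3% | 2.357 | 63.7% |

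**Step 3: sensitivity.** For the 0.6-point bias, moving the SD from 4 to 2 gives 12% to 36% at n=30 and 18% to 55% at n=50. If the SD of 3 excludes the spread that the side gap itself adds, the total SD becomes √(9 + s²(1 − (2q − 1)²)). At the high end that is √(9 + 4 × 0.75) = 3.46, and the probabilities fall to 33% (n=30) and 52% (n=50).

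**Step 4: order imbalance, if the draw is simple 1:1.** Exact binomial probabilities:
- n=30: 18:12 or worse, 36%; 20:10 or worse, 9.9%.
- n=50: 28:22 or worse, 48%; 30:20 or worse, 20%.

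The shift in the unadjusted mean difference is the visit effect × (difference in order counts) / n. For an assumed 1-point visit effect this is 10/30 = 0.33 at 20:10 and 10/50 = 0.20 at 30:20. Over repeated draws it averages to zero. In simulation (40,000 trials per setting, SD 3, visit effects of 1 and 2 points) the overall type I error stayed at about 5%. Among trials with a difference of 10 or more in the order counts it was 9% to 18% at n=30 and 8% to 13% at n=50.

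**The case against.** The strongest reply is that silence is not evidence of a fault. The main points, and what stands of each:

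- **Sides may already be planned.** Children are chosen for their treatment need, and the appointment is made after the recruitment contact, so a treatment plan may exist before any draw. The documents therefore do not support inferring that sides are left open in practice, or that the operator steers them. What stands is that the plan does not require the sides to be set or recorded first.
- **Randomising only the order is not in itself a defect.** If the side sequence cannot depend on the draw, randomising order also randomises side to condition. This is correct, and the fix relies on it.
- **The draw may be blocked.** A random number generator can produce a blocked list, so a reader who infers an unblocked draw goes beyond the text.
- **The operator's role.** A reader might infer that she also recruits and schedules. The Recruitment section is mostly in the passive voice and says that the appointment is made with a named person, not by that person. Only treating, injecting and presenting the scale are needed for this point.
- **The side gap may be small.** Eligibility reads most naturally as one jaw per child, hence one injection type. Topical agent, needle type, anaesthetic and number of cartridges are the same at both visits, and pain is scored before restorative work. This favours the lower part of the range. It does not exclude mixed jaws, and it leaves side and tooth open.
- **Order imbalance is chance, not bias.** This is right. It should not be read as inflating the overall error rate.

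**Conclusion.** The gap is real and should be closed, with medium confidence about how much it matters. As written, the plan permits side to be matched to condition by an operator who knows the device state, and the planned paired comparison would not remove the resulting bias.

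The size is conditional. At SD 3, the probability that a device with no effect looks better runs from barely above nominal at a 0.2-point bias to many times nominal at 1.0 point. Side gap, degree of steering and SD are all assumptions, and the result also requires that the assignment be known before the side is chosen. Nothing in the documents shows that this happens.

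Order imbalance is secondary: it matters for the one realised allocation, and the analysis can adjust for it.

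**What to change.** 1. Before the assignment is revealed, record on the data form the side, tooth and injection type planned for visit 1 and for visit 2. The clinical plan stays with the clinician; only the time of recording changes.
2. Then reveal the assignment from a list made in advance and concealed from the operator. Sealed numbered envelopes held by the person who does the weekly fidelity checks would serve, provided that person is not the operator. State in the Methods section when the reveal takes place.
3. Log any later change of side or tooth as a deviation, and analyse the child under the assigned order.
4. Add a visit (period) term to the paired analysis.

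Blocking is optional. Blocks of 4 would hold the order counts within 2 of each other, so a 1-point visit effect could shift the mean by at most 2/30 = 0.07 or 2/50 = 0.04. But an operator who sees every past assignment could guess some later ones, more so if the list is also stratified by jaw. Blocking alone does nothing about side choice.

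The cost is one line on the form, a set of envelopes and a short amendment, with no extra children or staff. The small downside is that the side cannot be changed after the reveal without a logged deviation.

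### The DentalVibe is introduced to the child only at the ON appointment, so the ON-OFF difference measures vibration plus its introduction, not vibration alone

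*Combined protocol and SAP*

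**What the plan says.** Each child has two restorative appointments, one with the DentalVibe on and one with it off, and a random number generator decides which comes first (Methods).

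- **ON appointment.** Methods: "During the DentalVibe turned on appointment, the DentalVibe will be introduced to each child to make him/her familiar with the vibration sensation". The Informed Consent section says the same: "During the appointment when the DentalVibe injection system is turned on, the DentalVibe will be introduced to each child", the aim being to make "him/her familiar with the vibration sensation prior to use during local anesthetic injections". The step therefore comes before the injection and before the pain rating.
- **OFF appointment.** The same device is in the mouth but switched off: "Used strictly as a check/lip retractor". No introduction is described.
- **Common to both.** Methods holds the provider, assistant, room, clothing and topical anesthetic constant. On nitrous oxide it says "All subjects will receive nitrous during both restorative appointment due to the age of the subjects". The Informed Consent section adds: "Tell-show-do will be used as a behavior guidance technique during all dental appointments".
- **Second visit.** Methods: "The same process will be followed at the second appointment".

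The stated purpose contrasts injection with the DentalVibe against injection with it turned off. The introduction is not named as part of the experimental condition. The analysis is described only as descriptive statistics, t-tests and correlations.

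**The concern.** Using the same device, switched off, as the control holds retraction, setting and staff constant. A reader will naturally take what remains as the effect of vibration during the injection, which is the mechanism put forward in the Purpose, Background and Rationale section (gate theory). But the plan writes in a second difference: at ON the child is prepared for the device beforehand, and at OFF no such preparation is scheduled.

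The outcome is self-reported pain, and the same background section says that more anxious patients feel more pain. The protocol thus supplies a plausible route from preparation to the score. If ON scores are lower, the planned data cannot show how much is due to vibration and how much to the preparation, because every ON visit contains both. At stake is what a positive result may be called.

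**Working it through.** **Step 1: what differs between the appointments**

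| Component | ON | OFF |
|---|---|---|
| Device in mouth as retractor | yes | yes |
| Vibration during injection | yes | no |
| Introduction to device and vibration beforehand | yes (Methods, Informed Consent) | not written |
| Tell-show-do | yes | yes; device content not stated |
| Nitrous oxide, topical anesthetic, provider, assistant, room, clothing | yes | yes |

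Two rows differ, not one. The sentence on the second appointment does not fill the gap, because the introduction is tied to the ON appointment, whichever visit that is.

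**Step 2: does randomized order remove it?** Let v be the effect of vibration, i the effect of the introduction, c the fraction of i that carries over to a later OFF visit, and q the share of children treated ON first. Then

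E[ON - OFF] = v + i - q·c·i = v + i(1 - q·c).

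- No carry-over (c = 0): v + i.
- Full carry-over and half the children ON first (c = 1, q = 0.5): v + 0.5i.

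The introduction stays in the contrast whenever q·c < 1. Preparation at OFF also depends on order: ON-first children have met the device 3-4 weeks before, and OFF-first children have not. If the random numbers are unrestricted (assumption; no blocking is mentioned), the 95% binomial range for ON-first children is 10-20 of 30 or 18-32 of 50. With c = 1, the net share of i is then 1 - 20/30 to 1 - 10/30 = 0.33-0.67, or 1 - 32/50 to 1 - 18/50 = 0.36-0.64.

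**Step 3: how large a shift would matter?** The plan gives no SD, effect size, alpha or power, so there is no stated figure to reproduce. The sample sizes are 30 (Subjects) and up to 50 (Methods). Assume v = 0, complete data and a two-sided 5% paired t-test. With d = net shift / SD of the paired difference,

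P(significant) = P(|T| > t(0.975, n - 1)), where T is noncentral t with n - 1 df and noncentrality d·√n.

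Solving for 0.10, twice the nominal rate:

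- n = 30: critical value 2.045, d = 0.1231 (0.1231 × √30 = 0.674).
- n = 50: critical value 2.010, d = 0.0941 (0.0941 × √50 = 0.665).

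In FACES points, for assumed SDs of the paired difference:

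| SD (assumed) | n = 30 | n = 50 |
|---|---|---|
| 2 | 0.246 | 0.188 |
| 3 | 0.369 | 0.282 |
| 4 | 0.493 | 0.376 |

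Adjacent faces are 2 points apart. Dividing by 2 gives a net one-face change in 12.3-24.6% of children at n = 30, or 9.4-18.8% at n = 50. With c = 1 and q = 0.5, the introduction effect itself would have to be twice as large: 0.493-0.985 point at n = 30 and 0.376-0.753 point at n = 50.

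These are tipping points. The documents do not show that any introduction effect reaches them.

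**The case against.** **The comparison is of device use.** The purpose is stated as injection with the DentalVibe against injection with it off, and the Benefits section speaks of finding an effective device. No objective claims to isolate vibration, and a vibrating instrument would naturally be shown to a young child before use. This stands: the contrast is valid for device use. But the plan does not say that the introduction belongs to the condition, and the switched-off control invites the narrower reading.

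**Both visits already include preparation.** Tell-show-do applies at every appointment and may cover showing the device at OFF. That is possible but not written, whereas the vibration introduction is written twice as an ON step.

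**Nitrous oxide leaves little to shift.** It is given at both visits, and Methods says "It is used to reduce anxiety, produce analgesia, and enhance effective communication between a patient and health care provider". This is a fair reason to expect a small effect, though it does not show that there is none.

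**The remedy is partial.** A script that differs only in whether the device runs still leaves the child feeling vibration beforehand at ON alone, and familiarity with vibration is the step's stated purpose. A demonstration of a still device might also signal the inactive condition. This stands too, which is why the description of the comparison must change as well.

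**The size calculation is generic.** It would be the same for any unmatched step, and it counts significant results in either direction. Agreed: it sets a scale and is not evidence of harm.

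A reader might infer that a lower ON score would be an artifact of preparation, or that the trial is biased in favor of the device. The documents do not support that: they give no size and no sign for the introduction effect.

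**Conclusion.** The point holds in a limited form. As written, the introduction is scheduled at ON only, and the ON-OFF difference estimates vibration plus its introduction against device off. Randomized order does not remove this, and neither tell-show-do nor the sentence on the second visit supplies the missing step. The comparison is valid for device use; it is not a comparison of vibration alone.

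The size is unknown. Under the assumptions of no vibration effect, complete data and a paired t-test, a net shift of about an eighth of an SD at 30 children, or somewhat under a tenth at 50, would be enough to double the nominal 5% rate. The figures in points rest further on an assumed SD of 2 to 4.

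A reader might also infer that matching the introduction would make the trial a test of vibration alone. It would not, because prior familiarity with the vibration remains part of ON and is carried to OFF in ON-first children. The change should be made because it is cheap and must be in place before data are collected; afterwards only the label can be corrected. Confidence is medium.

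**What to change.** Do both of the following.

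1. In Methods and Informed Consent, replace the ON-only introduction with: *At both appointments, just before the injection, every child will receive the same scripted introduction to the DentalVibe, with the same wording and duration, differing only in whether the device is running.* This matches attention, explanation and preview of the device. If tell-show-do is meant to deliver it, say so there.
2. In the purpose statement and in the planned conclusion, describe the comparison as use of the vibrating device, including its pre-injection familiarization, against device off. This is needed even if the first change is made.

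**Cost.** A wording change in the two places that describe the introduction, one sentence on the comparison, about a minute more at the OFF appointment (assumption), and no extra staff.

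**Downsides.** The child still knows whether the device vibrates, and ON-first children have felt the vibration before OFF, so expectation effects are reduced and not removed. Methods calls the trial a systematic replication with three listed differences. If the replicated study had no such step at OFF, which cannot be checked from these documents, the step should be added to that list.
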